**Table 7-8 Power to detect a difference in prevalence by sample size and background prevalence**

| Target Sample Size (N) | Background Prevalence (P0) | Prevalence in Exposed (P1) | Difference Prevalence (P1 - P0) | Power*        |
|------------------------|----------------------------|----------------------------|---------------------------------|---------------|
| 300                    | 0.02                       | 0.04                       | 0.02                            | 0.5408        |
| 400                    | 0.02                       | 0.04                       | 0.02                            | 0.6363        |
| 500                    | 0.02                       | 0.04                       | 0.02                            | 0.7076        |
| 300                    | 0.03                       | 0.06                       | 0.03                            | 0.7207        |
| 400                    | 0.03                       | 0.06                       | 0.03                            | 0.8278        |
| 500             | 0.03                | 0.06                | 0.03                     | 0.8926 |
| 300             | 0.06                | 0.12                | 0.06                     | 0.9588 |
| 400             | 0.06                | 0.12                | 0.06                     | 0.9843 |
| 500             | 0.06                | 0.12                | 0.06                     | 0.9961 |

\*Derived using two-sided binomial exact test for one sample proportion at target  $\alpha=0.05$  (PASS v11.0.10)

## 7.6 Data management

This Kesimpta-PRIM study is based on pregnancy cases reported in the Novartis global safety database (Argus). Cases are followed-up using targeted FU checklists provided in [Annex 12.1](#). When a new case is created in Argus, it is assigned a unique Argus ID which allows information across data sets to be linked.

Data collected through the targeted checklists will be entered into the Novartis global safety database per Novartis standard operating procedures (SOPs) governing pharmacovigilance safety procedures and MAP. Concomitant or prior medications entered into the database will be coded using the World Health Organization (WHO) Drug Reference List. Medical history/current medical conditions and adverse events will be coded using the Medical dictionary for regulatory activities (MedDRA) terminology.

Specific database conventions and deviation to MAP for all information required in the PRIM FU checklists will be described in the product-specific PGD.

## 7.7 Data analysis

Novartis will perform all analyses using SAS version 9.4 (or above). A statistical analysis plan (SAP) detailing the analysis to be conducted for Kesimpta-PRIM will be developed prior to the first data lock point.

The primary Kesimpta-PRIM analysis cohort will constitute the prospectively-reported pregnancies associated with maternal exposure during pregnancy or up to 180 days before LMP. Since retrospective cases may be subject to reporting biases but still be informative, these will be analyzed and reported separately.

Note that comparison with external background data will only be performed for the primary cohort, due to the high risk of bias for retrospective reports.

Missing data will not be imputed.

Continuous variables will be summarized presenting number of non-missing values, mean, standard deviation, median and range; for categorical variables numbers and proportions will be reported among non-missing. When presented, the 95% confidence intervals for proportions will be constructed based on the exact (Clopper-Pearson) method.

Annual interim data will be provided as per Section 4 Milestones.

### 7.7.1 Analysis of primary and secondary endpoints

Analysis of the Kesimpta-PRIM data will include estimation of proportion (and 95% confidence interval) of malformations (major [primary endpoint], minor [secondary endpoint], and overall), and of specific pregnancy outcomes such as, spontaneous abortions, stillbirths and elective terminations. The proportion of congenital malformations will be calculated amongst: (1) live births; and (2) live births, stillbirths and TOPFA (termination of pregnancy for fetal anomaly). Proportion will be estimated overall and by pre-specified timing of drug exposure in pregnancy (as defined in [Section 7.3.1](#)).

In addition, major congenital malformations will also be summarized by SOC based on latest available MedDRA classification.

Minor congenital malformations will be listed by preferred term based on latest available MedDRA classification.

The proportion of **other adverse birth outcomes** associated with exposure to Kesimpta during pregnancy including preterm births, low birth weight and small for gestational age (SGA) will be estimated among live births.

The proportion of adverse effects with particular focus on serious infections in the infant during the first 12 months after birth will be provided.

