#### 4 Milestones

Annual interim reports of the Kesimpta-PRIM study will be submitted on a yearly basis as a standalone procedure. A final report of the results of the PRIM will be submitted to Health

Authorities and will be made public in the EU PAS Register according to the EU legislation and regulations.

The expected dates of study milestones, assuming a maximum duration of 10 years, are presented in [Table 4-1](#).

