**Table 7-2 Kesimpta-PRIM prospective and retrospective case classificationa**

| Timing and results of prenatal testing   | Kesimpta PRIM case classification |
|---|--|
| Pregnancy outcome has not occurred, and prenatal tests have not been performed at the time of reporting or entry b     | Prospective                              |
| Prenatal testing was performed at the time of entry b , results have not been received by provider/patient/Novartis    | Prospective                              |
| Prenatal test results were available, and were known to be normal or results were not specified at the time of entry b | Prospective                              |
| Prenatal test results were available and were known to be abnormal at the time of entry b                              | Retrospective                            |
| Outcome of pregnancy known at the time of entry b  | Retrospective                            |

a) Definitions of retrospective and prospective cases as per EMA guidance

b) 'Entry' is considered the date of initial report received by Novartis for this case

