### 7.7.3 Case description

The cohort attrition will be presented providing the overall vs. prospective vs. retrospective number of pregnancy cases and fetuses retrieved at the time of the analysis cut-off date via maternal and paternal exposure.

In addition, the following information will be summarized

- Case disposition status (outcome known, pending, and lost to follow-up),
- Maternal characteristics (age (continuous), country/region),
- Reporter type (Health Care Professional (HCP), non-HCP).

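### The crude proportion for spontaneous abortion ignores gestational age at first report, so it understates risk, and the first interim reports may be inflated while births are pending

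*Protocol*

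**What the plan says.** Section 7.7.1 plans "estimation of proportion (and 95% confidence interval) of malformations" "and of specific pregnancy outcomes such as, spontaneous abortions, stillbirths and elective terminations". Section 7.7 specifies that "the 95% confidence intervals for proportions will be constructed based on the exact (Clopper-Pearson) method", that "for categorical variables numbers and proportions will be reported among non-missing", and that "Missing data will not be imputed". Section 7.7.1 gives denominators for malformations and birth outcomes but none for spontaneous abortion.

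On entry, the footnote to Table 7-2 reads "Entry' is considered the date of initial report received by Novartis for this case". The table sets no gestational-age limit. A report made after a normal prenatal test is still prospective; a report made once the outcome is known is retrospective. Table 7-4 confines spontaneous abortion to before 22 weeks.

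On timing, Table 7-1 schedules a baseline contact and then none until the window from EDD to EDD + 30 days. Section 4 states that "Annual interim reports of the Kesimpta-PRIM study will be submitted on a yearly basis", with nine interim reports before the final one. Section 7.7.3 tabulates "Case disposition status (outcome known, pending, and lost to follow-up"), but nothing links that table to the estimates.

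**The concern.** A binomial proportion treats every pregnancy as having had the same opportunity to show the event. Here that fails by design. A woman first reported at week 20 cannot contribute the losses that occur earlier, yet she counts as much in the denominator as a woman reported at week 5. Pregnancies lost before anyone reported them are not in the cohort at all. The figure therefore depends on when women report, and it errs downwards, which is the unfavourable direction in a safety study.

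A second mechanism works the other way. A loss can be known months before a birth at 37 to 42 weeks. If pending pregnancies are left out of the denominator, an early data cut holds too many losses relative to births.

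The primary cohort is to be set against external background data, and the interim reports go to the regulator. A figure shaped by report date and cut-off date is hard to read in either setting.

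**Working it through.** The protocol states no figure for spontaneous abortion. Its only calculation, Table 7-8, concerns malformations and does not bear on this point. What follows is illustration; the risk and the entry pattern are assumptions.

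**Model.** Weekly hazard h(w) = c·exp(−0.22(w − 5)) for weeks 5 to 21, with c = 0.0326 so that the cumulative risk is 15%. With S(e) the probability of still being pregnant at week e, S(22) = 0.85 and the risk remaining at entry is R(e) = 1 − 0.85/S(e).

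| Entry week | S(e) | R(e) |
|---|---|---|
| 5 | 1.000 | 15.0% |
| 6 | 0.967 | 12.1% |
| 8 | 0.922 | 7.8% |
| 12 | 0.877 | 3.1% |
| 20 | 0.852 | 0.2% |

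**Delayed entry, complete follow-up.** If potential entry is spread evenly over a set of weeks, the crude proportion is Σ[S(e) − 0.85] / ΣS(e).
- Weeks 5 to 12: (7.396 − 8 × 0.85)/7.396 = 8.1%.
- Weeks 5 to 20: (14.271 − 16 × 0.85)/14.271 = 4.7%.

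A second model gives the same picture (15% risk over weeks 4 to 22, lognormal entry). Median entry at week 6, 8, 10 or 12 yields a crude 9.7%, 6.8%, 4.9% or 3.6%, against a true week 6 to 22 risk of 10.2%. A left-truncated Kaplan-Meier estimate recovers the truth to within 0.1 point in each case.

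**Pending births, one entry week.** Take entry at week 8 (remaining risk q = 7.8%), loss known at week 11, birth known at week 42 and even accrual over T years. The known fractions are k_s = 1 − 3/(52T) for losses and k_b = 1 − 34/(52T) for births. The apparent proportion is q·k_s / [q·k_s + (1 − q)·k_b].

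| T (years) | k_s | k_b | Apparent proportion |
|---|---|---|---|
| 1 | 0.942 | 0.346 | 18.8% |
| 2 | 0.971 | 0.673 | 10.9% |
| 5 | 0.988 | 0.869 | 8.8% |

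**Both effects together.** With the same hazards, entry spread continuously through weeks 5 to 12 and losses known as they occur, the figure is about 16% at one year, 10% at two and 8% from five. The second model with median entry at week 8 gives 15.4%, 9.2%, 8.2%, 7.6% and 7.1% at 1, 2, 3, 5 and 10 years. If every outcome is instead recorded only about two weeks after EDD, that model stays at 6.2% to 6.7% and the drift nearly vanishes.

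**Primary proportion (ii).** Assume termination for fetal anomaly (TOPFA) in 0.3% to 1% of pregnancies, known at week 22, with 3% malformations among births, entry at week 8 and no stillbirths. At T = 1 the known fraction is 1 − 14/52 = 0.731 for TOPFA and 0.346 for births. With 1% TOPFA the proportion is (0.01 × 0.731 + 0.03 × 0.99 × 0.346)/(0.01 × 0.731 + 0.99 × 0.346) = 5.0%, against a true 0.01 + 0.03 × 0.99 = 4.0%. With 0.3% it is 3.6% against 3.3%. By year 5 the excess is at most 0.1 point.

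**The case against.** The other side has several good points.

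- **Section 7.9 already limits the comparison.** It warns that comparison with external references, for malformations and other outcomes, is hampered by differences in data collection. The study is descriptive, with no hypothesis and no measure of association. This stands as a general caution. But Section 7.9 names immortal time only for the stratum exposed only after the first trimester, not for gestational age at entry, which affects the whole cohort.
- **Excluding pending cases is an inference.** No denominator is given for spontaneous abortion; the reading rests on the general non-missing rule. An analysis plan could set a maturity rule or add a left-truncated analysis. That weakens the drift argument but not the delayed-entry argument, because the protocol itself commits to the crude proportion.
- **Drift needs early reporting of losses.** The only scheduled outcome contact is at EDD to EDD + 30 days. Patients and clinicians may report at any time, so earlier notice is plausible, but it is not certain.

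A reader might also infer that a 15% risk would show as 33% at one year. That applies the week 5 risk to women who enter at week 8, when only 7.8% remains; the matching figure is about 19%. Nor would a trend across all nine interim reports be mostly artefact: the effect is concentrated in the first two or three.

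**Conclusion.** The point holds for spontaneous abortion, a secondary outcome. The downward bias from delayed entry follows from what the protocol fixes. Its direction is sure; its size depends on the assumed risk and on when women report. Under a 15% risk over weeks 5 to 21 the crude figure is roughly 8% or 5% for the two entry patterns shown.

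The upward drift is conditional on losses being notified before the EDD contact and on pending cases being left out of the denominator. On those terms it roughly doubles the first annual figure and then fades.

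A reader might conclude that the primary endpoint is compromised. The documents do not support that. Proportion (i) is confined to live births and contains no terminations. Any effect on proportion (ii) is likely small and short-lived: 0.3 to 1.0 point at one year under the assumptions above, and close to nil by year five. Table 7-8 is unaffected.

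**What to change.** 1. At each data cut, restrict the pregnancy-outcome proportions, and primary proportion (ii), to pregnancies whose EDD + 30 days falls before the cut-off.
2. In that same mature cohort, estimate the cumulative incidence of spontaneous abortion to 22 weeks on the gestational-age scale, with delayed entry at gestational age on the initial report date and terminations as a competing event (Aalen-Johansen with left truncation). Start from the earliest week with an adequate risk set. The method cannot recover risk before that week, and it assumes that the timing of a report is unrelated to later loss.
3. Do not censor pending cases at last contact. No contact is scheduled between baseline and EDD, so many would be censored at entry while early losses still count. In the model above that gives about 29% at one year and 17% at two, against a true week 6 to 22 risk of 12.1%. The mature-cohort version returns 12.0% to 12.2%.
4. Report cases lost to follow-up separately, with a sensitivity analysis.
5. Report gestational age at entry, and state in Section 7.9 that the crude proportion is subject to delayed-entry bias.

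The cost is wording and standard programming; report date, LMP or EDD and outcome date are already collected. Cases without LMP or EDD drop out of this analysis. Early reports rest on fewer pregnancies: taking EDD as 40 weeks, entry at week 8 needs 40 + 30/7 − 8 = 36.3 weeks to mature. Under even accrual, 1 − 36.3/52 = 30% of cases are mature at one year, 1 − 36.3/104 = 65% at two and 1 − 36.3/260 = 86% at five.

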### 7.3.1 Exposure

Trimesters will be defined, based on the dose administered, as follows:

- “Peri-LMP”: LMP- 180 days to LMP,
- “1st trimester”: LMP to LMP+84 days,
- “2nd trimester”: LMP+85 days to LMP+182 days,
- “3rd trimester”: LMP+183 days and beyond.

Cases will be classified by timing of Kesimpta exposure i.e. as “Overall” vs. “Peri-LMP only” vs. “At least 1st trimester” vs. “Only after 1st trimester”.

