**Table 7-4 Definition of key pregnancy outcomes**

| Outcome                                | Definition   |
|--|--|
| Full-term live birth                   | The patient gives birth to live neonate between 37 and 42 completed weeks of gestation.  |
| Premature live birth **                | The patient gives birth to a live neonate before 37 completed weeks of gestation.  |
| Post-mature live birth                 | The patient gives birth to a live neonate after 42 completed weeks of gestation  |
| Elective termination **                | Termination of pregnancy due to choice of mother of an otherwise normal fetus.   |
| Therapeutic termination                | If an abortion procedure occurs due to abnormal fetus, fetal death or risk to the mother.  |
| Spontaneous abortion **                | The fetus is spontaneously aborted (prior to 22 weeks gestation); prior fetal status via prenatal testing may or may not be known.   |
| Stillbirth **                          | The patient gives birth to a still born (no signs of life) at or after 22 weeks of gestation is completed  |
| Abortion not otherwise specified (NOS) | Used in cases where spontaneous / elective / therapeutic abortion is not specified. (NOTE: If abortion is performed due to maternal or fetal complications, this case is classified as "Therapeutic abortion") |
| Outcome pending                        | The outcome of the pregnancy is not known (outcome/due date is pending, or queries are outstanding)  |
| Lost to F/U                            | No further information is received regarding pregnancy outcome even after pursuing appropriate number of follow-ups for a case   |

\*\* To be used in the analysis of the secondary outcomes

Source: Manual for Argus Processing - MAP chapter 13 Pregnancy cases, version 10.2, effective 15Jul2021

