## 7.9 Limitations of the research methods

The limitations of PRIM are detailed by [Geissbühler et al \(2020\)](#) and are consistent with those of voluntary post marketing report systems: under reporting, and a potential for more missing or incomplete information than in a clinical study. Spontaneous report data are collected passively relying on healthcare professionals and patients to recognize suspected adverse outcomes, collect and collate relevant information, and submit reports in the required format. Hence, the information received is often insufficient or incomplete. To reduce the potential for selection bias due to loss to follow-up (a recognized limitation of voluntary reporting systems), contact attempts via multiple contact modalities are systematically and repeatedly performed under the PRIM processes. In addition, prospective cases (where pregnancy outcome is unknown at the time of reporting) and retrospective cases will be evaluated separately given the risk of selective reporting of adverse outcomes in retrospective reporting.

A direct comparison between prevalence estimates of congenital malformation and other outcomes obtained through PRIM with external reference in the general populations is hampered by potential differences in data collection methods. Interpretation of the results of these comparisons is therefore limited. Nevertheless, the results can be put in context with a range of estimates from the general population coming from different data sources with a focus on those which use similar data collection methods as PRIM ([Geissbühler et al 2020](#)).

To evaluate the impact of exposure on the pregnancy outcomes further, exposure is stratified as exposure during peri-LMP only vs exposure only after 1st trimester. These categories may, however, be subject to selection bias. The group “exposure during peri-LMP only” excludes pregnancies with normal outcomes without any assessment of drug exposure duration (i.e., throughout the entirety of the pregnancy). On the other hand, the group “exposure only after 1st

trimester” could be subject to immortality bias. By construction, the category would not capture any event prior to 1st trimester of exposure.

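### The late-exposure class cannot contain a loss before day 85, so its crude spontaneous-abortion proportion is understated against the other classes; Section 7.9 discloses this but nothing repairs it

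*Protocol*

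**What the plan says.** Section 7.7.1 plans estimates with 95% confidence intervals for malformations "and of specific pregnancy outcomes such as, spontaneous abortions, stillbirths and elective terminations". After giving the malformation denominators it adds: "Proportion will be estimated overall and by pre-specified timing of drug exposure in pregnancy". Section 7.7 makes the interval for any proportion Clopper-Pearson.

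The timing classes are in Section 7.3.1: "Cases will be classified by timing of Kesimpta exposure", giving *Overall*, *Peri-LMP only*, *At least 1st trimester* and *Only after 1st trimester*. The first trimester is "LMP to LMP+84 days" and the second is "LMP+85 days to LMP+182 days".

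Table 7-4 defines spontaneous abortion: "The fetus is spontaneously aborted (prior to 22 weeks gestation"). Twenty-two weeks is day 154.

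Section 7.9 says what the strata are for: "To evaluate the impact of exposure on the pregnancy outcomes further, exposure is stratified as exposure during peri-LMP only vs exposure only after" the first trimester. It warns that the late class could be subject to immortality bias and gives the mechanism: "By construction, the category would not capture any event prior to" the exposure that defines the class.

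**The concern.** Class membership is settled by looking back over the whole pregnancy, while the outcome is counted from its start. A pregnancy lost on day 60 may belong to *Peri-LMP only* or *At least 1st trimester*, but never to *Only after 1st trimester*, because it ended before a qualifying dose was possible. Any denominator built from the late class therefore holds only pregnancies that had already passed the first part of the risk window.

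For spontaneous abortion the words *could be* in Section 7.9 are too weak: exclusion of losses before day 85 follows from the definitions. The same holds for elective terminations before day 85.

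At stake is how the stratified table is read. It would put a low loss proportion for late exposure beside higher ones for earlier exposure, and Section 7.9 sets out that contrast as a way to evaluate the impact of exposure. A drug with no effect on pregnancy loss could produce the same pattern.

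**Working it through.** **The plan's own figure.** The protocol states none for spontaneous abortion. Its one calculation, Table 7-8, reproduces in all nine rows (0.8926 for 500 live births, 3% against 6%) but concerns malformations and does not bear on this point.

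**Inputs from the protocol.** Earliest qualifying dose for the late class: day 85 (7.3.1). Window for spontaneous abortion: before day 154 (Table 7-4). Prospective cases must be ongoing at the initial report (Table 7-2), and they form the primary cohort (7.2, 7.7).

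**At-risk time.** The late class can show a loss only on days 85 to 153, which is 154 − 85 = 69 of 154 days (45%).

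**Assumed inputs.** Total loss R = 15%. Share s of losses before day 85 is 60%, 80% or 90%. Early losses are uniform over days 42–85 and later ones over days 85–154. Report day is uniform over days 28–140 in every class. There is no drug effect, and dose and report timing are unrelated to loss.

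**Formula.** Let r(x) be the probability of a loss after day x:
- before day 42, r = R
- days 42–85, r = R·s·(85−x)/43 + R(1−s)
- days 85–154, r = R(1−s)(154−x)/69
- from day 154, r = 0

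If a pregnancy must be ongoing at day x to be counted, the loss proportion is A/(A + 1 − R), where A is the average of r over the distribution of x.

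*Other classes* (x = report day): A = R[14 + 43(1 − s/2) + 33.08(1−s)]/112, where 33.08 = (69² − 14²)/(2·69). For s = 0.8: A = 0.15 × 46.42/112 = 0.0622, so 0.0622/0.9122 = 6.8%.

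*Late class, all doses on day 85* (x = later of report and day 85): A = R(1−s)(57 + 33.08)/112 = 0.804·R(1−s). For s = 0.8: 0.0241/0.8741 = 2.8%.

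*Late class, first late dose uniform over days 85–280* (x = later of report and dose): A = 0.1585·R(1−s), by integrating the product of the two distribution functions over days 85–154 and dividing by 69. For s = 0.8: 0.00476/0.85476 = 0.56%.

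| Share lost before day 85 | Other classes | Late class, doses on day 85 | Late class, doses to day 280 |
|---|---|---|---|
| 60% | 8.3% | 5.4% | 1.1% |
| 80% | 6.8% | 2.8% | 0.6% |
| 90% | 6.1% | 1.4% | 0.3% |

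The smallest relative understatement is 1 − 5.4/8.3 = 35%; the largest is 1 − 0.28/6.06 = 95%. A simulation of 4,000,000 pregnancies agrees. Starting early losses at day 28 instead of 42 moves the other classes to 5.2–7.7% and leaves the late class unchanged.

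**When the contrast vanishes.** If every pregnancy is reported at day 100 and every late dose falls on day 85, all classes are conditioned on reaching day 100. For s = 0.8, r(100) = 0.03 × 54/69 = 0.0235, and 0.0235/0.8735 = 2.7% in every class.

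**Does a day-85 landmark cure it?** Everyone in the late class is already ongoing at day 85, so a landmark leaves its numerator and denominator unchanged. Without a report condition, s = 0.8 and doses spread to day 280, the class shows 0.6% before and after the landmark. All pregnancies ongoing at day 85 show 0.15 × 0.2/(1 − 0.15 × 0.8) = 3.4%. Immortal time from day 85 to the first dose remains.

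**The case against.** The strongest reply is that the protocol already says this. Section 7.9 names the bias for exactly this class, states its mechanism and warns about the peri-LMP class too. The study is descriptive, with no hypothesis tests or measures of association (Annex 2). The Abstract makes subgroup analysis by timing conditional on sample size, Section 7.9 accepts that some secondary analyses may not be possible, and the SAP is not shown. All of that stands and limits the weight. It does not remove the point: Section 7.7.1 states a proportion by class, and an analysis that follows it carries the bias.

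The timing sentence in 7.7.1 can also be read as covering malformations only, because it follows the malformation denominators. Section 7.9 favours the wider reading without settling it.

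Three stronger readings go too far.
- A reader might set the late class against a full 15% loss risk, giving 0.6% against 15.0%. The primary cohort must be ongoing at report, which lowers the other classes as well.
- A reader might hold that the problem is separate from reporting time and would persist if all pregnancies were reported at the same gestational age. It need not: the day-100 example shows no contrast.
- A reader might say that the other classes are inflated. This mechanism does not inflate them; one class is understated.

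**Conclusion.** The point holds as a bias that is disclosed but not repaired. That losses before day 85 cannot enter the late class follows from Sections 7.3.1 and 7.7.1 and Table 7-4 alone. The resulting understatement relative to the other classes, under no drug effect, also needs report timing to be similar across classes.

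Its size cannot be taken from the protocol. Under the stated assumptions the late class shows about 0.3–5.4%, depending mainly on dose timing, against about 6–8% elsewhere. The contrast shrinks or vanishes if all pregnancies are reported after day 85 and late doses precede the report. No size was worked out for elective termination; the same exclusion applies to those before day 85.

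The consequence is a misleading secondary table. The primary endpoint and the study-size rule are not affected. The amendment is worth making before the stratified table is produced.

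**What to change.** Amend Section 7.7.1 so that spontaneous abortion and elective termination are reported overall and are not tabulated as crude proportions by exposure class. If the timing sentence was meant for malformations only, saying so is enough.

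If results by timing are wanted, treat exposure as time-varying with delayed entry. Each pregnancy contributes to a class only from the later of its report date and the dose that places it there. Give cumulative incidence or rates over the same gestational window in every class. A day-85 landmark alone is not enough while class membership depends on doses after day 85. The interval method must be named, because the Clopper-Pearson rule in Section 7.7 is for simple proportions.

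The cost is wording and modest programming. Table 7-3 already collects medication start and stop and gestational weeks at termination, and Table 7-2 defines entry as the date of initial report. One check is needed first: Section 7.4 has trimester of exposure entered as a tick box and Section 7.3.2 keeps some variables as free text, so confirm that dose dates can be extracted. The downside is few events in a class that may be small.
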